All electronic data files for this study will either be stored as password-protected files on an encrypted, password-protected computer, in the Yale Clinical Trials Management System (OnCore), or on the limited-access secure Yale ITS server. OnCore is accessed through Yale-networked computers and access is granted only to appropriate study personnel. Any files that contain protected health information will be maintained separately from the rest of other data files and only on the secure server or in OnCore.

The research database that contains the participant data will be maintained on the secure Yale server and will be de-identified at the end of the study. Access to this database will be restricted to the small subset of individuals responsible for study operations. In this manner, we hope to minimize the risk of breach of confidentiality by limiting access to the PHI and its link to the anonymous unique identifiers.

e. What will be done with the data when the research is completed? Are there plans to destroy identifiable data?

At the end of the study, personally identifiable data in the research database will be de-identified or deleted using specific software to “securely” delete a selective file. Information regarding this software will be obtained from ITS at the time that it is needed. Personally identifiable data that exists in OnCore cannot be de-identified or destroyed. Access to the OnCore data will remain restricted.

f. Who will have access to the protected health information (such as the research sponsor, the investigator, the research staff, all research monitors, FDA, Yale Cancer Center Data and Safety Monitoring Committee (DSMC), SSC, etc.)? (please distinguish between PHI and de-identified data)

All of our paper survey forms will be stored in a single locked file cabinet located in the Department of Surgery. Access to the file cabinets will be limited to [name], PI of the study, and [name], Administrative Coordinator of the study.

All electronic data will be kept either in the Yale OnCore clinical trials management system or on secure Yale servers with access limited to study personnel. PHI in OnCore cannot be destroyed or de-identified; access to the OnCore data is restricted. PHI in the research database will be de-identified after the study conclusion. This anonymized research data will be maintained on the secure Yale server.

g. If appropriate, has a [Certificate of Confidentiality](#) been obtained?

We are not collecting data that would require a Certificate of Confidentiality.

h. Are any of the study procedures likely to yield information subject to mandatory reporting requirements? (e.g. HIV testing – reporting of communicable diseases; parent interview - incidents of child abuse, elderly abuse, etc.). Please verify to whom such instances will need to be reported.

No.

SECTION IX: POTENTIAL BENEFITS

Potential Benefits: Identify any benefits that may be reasonably expected to result from the research, either to the subject(s) or to society at large. (Payment of subjects is not considered a benefit in this context of the risk benefit assessment.)

An ongoing debate exists as to the optimal management of patients with PTMC. Options vary from total thyroidectomy to thyroid lobectomy to observation only. Many patients undergo total thyroidectomy; it is considered the standard-of-care treatment in the United States. However, morbidity is a concern in thyroid surgery. Surgical complications, such as hoarseness or hypoparathyroidism, and postoperative metabolic/psychological disturbances (that can occur in spite of adequate hormone replacement) can profoundly impact patient quality of life. It has been shown that the majority of patients with PTMC can be followed safely with observation close surveillance, without a significant difference in patient outcome. The option of percutaneous ethanol ablation allows for actual treatment of the

cancer, which is an advantage over observation, but it is considerably less invasive than total thyroidectomy.

We are offering a new treatment option for patients with PTMC, which could fundamentally change patient management. Percutaneous ethanol ablation is an established tool for the management of metastatic thyroid cancer or patients with benign primary thyroid conditions who are not ideal surgical candidates. By introducing this approach for patients with PTMC, we can potentially change current patient management and avoid the more invasive procedure in many patients (i.e. total thyroidectomy) by treatment of the cancer with a minimally invasive and low risk intervention.

SECTION X: RESEARCH ALTERNATIVES AND ECONOMIC CONSIDERATIONS

1. **Alternatives:** What other alternatives are available to the study subjects outside of the research?

Total thyroidectomy, thyroid lobectomy, or observation (observation is currently only performed as part of a protocol).

2. **Payments for Participation (Economic Considerations):** Describe any payments that will be made to subjects, the amount and schedule of payments, and the conditions for receiving this compensation.

None

3. **Costs for Participation (Economic Considerations):** Clearly describe the subject's costs associated with participation in the research, and the interventions or procedures of the study that will be provided at no cost to subjects.

The treatment in this study may be considered standard of care and it is anticipated that the patient's health insurance will cover all expenditures for the procedure, i.e percutaneous ethanol ablation. The follow-up visits will be performed by an endocrine surgeon from our department and the follow-up tests and visits are routine tests that are standard of care for surveillance of PTC.

4. **In Case of Injury:** This section is required for any research involving more than minimal risk.

a. Will medical treatment be available if research-related injury occurs?

Yes

b. Where and from whom may treatment be obtained?

If a patient is injured as a direct result of this research, he/she will receive treatment. The study investigators will assist in the coordination of care with caregivers close to the subject's residence. The patient or their health insurance will be expected to cover the cost of the treatment. No additional compensation for injury or lost wages is provided.

c. Are there any limits to the treatment being provided?

There are no limitations.

d. Who will pay for this treatment?

The patient or their health insurance.

e. How will the medical treatment be accessed by subjects?

Patients are instructed to call our office (available 24/7) with any questions or concerns.

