Patients in the PEA group will constitute the sole treatment group of the study. These patients will be scheduled for an outpatient procedure with [name] from Interventional Radiology. The volume of 99% ethanol to be injected is calculated using a standardized formula (Ethanol Volume= length × width × height × π / 6) and instilled with a 3-4 cm long 22-25-gauge needle under ultrasound-guidance after administration of local anesthesia. If the patient cannot tolerate the procedure despite adequate local anesthesia, they will be offered conscious sedation. Conscious sedation is a combination of medicines to help you relax (a sedative) and to block pain (an anesthetic) during a medical. You will probably stay awake but may not be able to speak.

It is usually safe, however, overmedication could result in respiratory depression. The patient will be monitored carefully during the entire procedure and the appropriate equipment will be employed if needed.

The procedure itself usually takes only about 60-90 minutes and the patient will be observed for 2-3 hours in the hospital before discharge home.

All patients will receive a phone call to their home 48 hours after the PEA procedure and will be assessed for pain level and voice quality (BPI and VHI).

Every patient will be scheduled for a post-procedure visit in the endocrine surgery clinic approximately 7 – 14 days after their procedure. The post-procedure clinic visit will include the following assessments:

- a) Evaluation of the wound after the intervention
- b) Follow-up ultrasound assessment
- c) Follow-up laryngoscopy after treatment
- d) Follow-up quality of life assessment (SF-36)
- e) Follow-up pain assessment (BPI)
- f) Follow-up voice assessment (VHI)
- g) Follow-up symptom assessment (TSQ)
- h) Cosmesis assessment (“Patient and Observer Scar Assessment Scale”, POSAS; Appendix 5)

During this clinic visit, a thorough evaluation will be performed of the patient's injection site. An endocrine surgeon will evaluate the injection site during this visit using POSAS, a validated tool for the evaluation of surgical scars [49-52].

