Descriptive statistics, including mean and standard deviation for continuous variables and frequency and percentage for categorical variables, will be used to summarize patient characteristics. The adverse events will be investigated in order to assess the safety of the new procedure. The primary analysis will be comparing the pre-operative TSQ score to the post-operative TSQ score. Using standard deviation of 6.38 as reported in the DEPTH (DEPression and THyroid) study [54], the sample size of 16 achieves 90% power to detect a difference of 5.65 between pre- and post-PEA with a type I error of 0.05 using a paired t-test. This effect size is equivalent to one-level difference in responses for 6 items (such as from "Much worse" to "Little worse"), or three-level differences in responses for 2 items (such as from "Much worse" to "Much better"), etc.

Similarly, a power analysis was performed for QOL. The Physical Component and Mental Component of SF-36 will be used. The standard deviations, 9.7 and 11.0 for patients with thyroid disease, respectively, were used to estimate statistical power. The sample size of 16 in each group achieves 90% power to detect a difference of 8.6 in SF-36 Physical Component summary score and 9.8 in Mental Component summary score between the PEA and thyroidectomy groups with a type I error of 0.05.

Time and motion studies and a cost analysis will also be conducted.

SECTION VI: RESEARCH INVOLVING DRUGS, BIOLOGICS, RADIOTRACERS, PLACEBOS AND DEVICES

If this section (or one of its parts, A or B) is not applicable, state N/A and delete the rest of the section.

A. DRUGS, BIOLOGICS and RADIOTRACERS

1. Identification of Drug, Biologic or Radiotracer: What is (are) the **name(s)** of the drug(s) biologic(s) or radiotracer(s) being used? Identify whether FDA approval has been granted and for what indication(s).

Percutaneous ethanol injection is approved by the FDA and is a well-accepted treatment modality for the management of metastatic thyroid carcinoma to the neck, as well as benign thyroid cysts or autonomic nodules [27, 28, 30-32, 36, 55]. The injection of ethanol has been also used successfully in the cure of liver tumors [56-61].

1. Hay, I.D. and J.W. Charboneau, The coming of age of ultrasound-guided percutaneous ethanol ablation of selected neck nodal metastases in well-differentiated thyroid carcinoma. *J Clin Endocrinol Metab*, 2011. 96(9): p. 2717-20.

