Stores the investigational device according to the manufacturer's recommendations with respect to temperature, humidity, lighting, and other environmental considerations:

Ensures that the device is stored in a secure area with limited access in accordance with applicable regulatory requirements:

Distributes the investigational device to subjects enrolled in the IRB-approved protocol:

SECTION VII: RECRUITMENT/CONSENT AND ASSENT PROCEDURES**1. Targeted Enrollment: Give the number of subjects:**

- a. Targeted for enrollment at Yale for this protocol: 40
- b. If this is a multi-site study, give the total number of subjects targeted across all sites
N/A

2. Indicate recruitment methods below. Attach copies of any recruitment materials that will be used.

 Flyers	 Internet/Web Postings	 Radio
 Posters	 Mass E-mail Solicitation	 Telephone
 Letter	 Departmental/Center Website	 Television
 Medical Record Review	 Departmental/Center Research Boards	 Newspaper
 Departmental/Center Newsletters	 Web-Based Clinical Trial Registries	
 YCCI Recruitment database	 Clinicaltrials.gov Registry (do not send materials to HIC)	
 Other (describe): Patients who meet eligibility criteria will be approached by an attending surgeon at Yale Endocrine Surgery and will be asked about their interest in enrollment into the study.		

3. Recruitment Procedures:

- a. Describe how potential subjects will be identified.

A letter will be sent to referring endocrinologists to raise awareness for this clinical trial. This letter will inform the endocrinologists about the general study purpose, study design, and potential inclusion and exclusion criteria. All potential patients will be referred to Yale Endocrine Surgery for final assessment of eligibility. We include a copy of this letter with the amendment form.

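### The power statement is built on 16 patients but enrolment is set at 40, so the plan does not state the power of the trial it will run or the basis for its size

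*Combined protocol and SAP*

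**What the plan says.** Section V.12 (Statistical Considerations) names the TSQ at the 12-month visit as the primary endpoint and a before/after comparison as the primary analysis. For that analysis it states that "the sample size of 16 achieves 90% power to detect a difference of 5.65 between pre- and post-PEA". The test named is a paired t-test, at the 0.05 level. The SD is taken from an outside study: "Using standard deviation of 6.38 as reported in the DEPTH".

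The same section then gives power for quality of life: "The sample size of 16 in each group achieves 90% power to detect a difference of 8.6 in SF-36 Physical Component summary score". The groups compared are PEA and thyroidectomy, and the corresponding Mental Component difference is given as 9.8 points.

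Section VII.1 (Targeted Enrollment) gives "Targeted for enrollment at Yale for this protocol: 40" and marks the multi-site total as not applicable. Section V.3 (Research Plan, Therapy) says: "Patients in the PEA group will constitute the sole treatment group of the study". All 40 patients would therefore receive PEA.

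The number 40 does not appear in Section V.12. Safety and feasibility are a secondary aim there, with no precision target or patient number attached. Loss to follow-up is mentioned only in Section VIII, as a reason for collecting identifiers.

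**The concern.** A reader who wants the power of this trial finds a figure for 16 patients and an enrolment target 2.5 times as large (40/16), with nothing connecting them. Two things follow.

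- **The design figure.** The 90% power and 5.65-point difference belong to a trial of 16 evaluable patients. They are not the power or the detectable difference at 40, or at any plausible number of completers from 40.
- **The basis for exposure.** The protocol says PEA has not been used before for primary papillary thyroid cancer, and it grades the study as greater than minimal risk. A committee asked to approve 40 treated patients sees a numerical argument for 16 only.

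**Working it through.** **Inputs.** From Section V.12: n = 16, difference 5.65, SD 6.38, type I error 0.05, paired t-test; for SF-36, differences 8.6 and 9.8 with SDs 9.7 and 11.0. From Section VII.1: enrolment 40. Two assumptions are needed because the plan is silent: the test is two-sided, and 6.38 is the SD of the within-patient change.

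**Method.** Exact paired t-test power from the noncentral t distribution, with n − 1 degrees of freedom and noncentrality (difference/SD) × √n.

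**Step 1: reproduce the plan's figure.** 5.65/6.38 = 0.886, and 0.886 × √16 = 3.54. Power is 91.1%. With n = 15 it is 89.0%, so 16 is the smallest number that reaches 90%. The plan's figure reproduces.

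**Step 2: the same inputs at the enrolment target.**

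| Evaluable patients | Power for 5.65 points | TSQ difference detectable with 90% power |
|---|---|---|
| 16 | 91.1% | 5.54 |
| 20 (half of 40 lost) | 96.4% | 4.88 |
| 32 (20% of 40 lost) | 99.8% | 3.77 |
| 40 | 99.98% | 3.35 |

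The loss rates are illustrations; the plan gives none.

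**Step 3: could attrition explain the gap?** Enrolment needed = 16/(1 − loss). Losses of 10%, 20% and 30% need 18, 20 and 23 patients. To arrive at 40 the loss would have to be 1 − 16/40 = 60%.

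**Step 4: could the unstated nature of the SD explain it?** If 6.38 is the SD of a single score, the SD of the change is 6.38 × √(2(1 − ρ)) for a pre/post correlation ρ. For assumed ρ of 0, 0.25, 0.5 and 0.75, the number needed for 90% power is 29, 23, 16 and 9. The plan's 16 corresponds to ρ = 0.5 on this reading. None of these values gives 40.

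**Step 5: could safety explain it?** With zero events among n patients, the two-sided 95% upper limit is 1 − 0.025^(1/n): 20.6% at n = 16 and 8.8% at n = 40. At the 3.9% dysphonia rate quoted in the protocol, the chance of seeing at least one case is 1 − 0.961^n: 47% at 16 and 80% at 40. This would be a reasonable argument for more than 16, but the plan does not make it.

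**Step 6: the SF-36 statement.** As written, with two groups of 16, the noncentrality is (8.6/9.7) × √(16/2) = 2.51 for the Physical Component and (9.8/11.0) × √(16/2) = 2.52 for the Mental Component, on 30 degrees of freedom. Power is 68.0% and 68.4%, not 90%; 90% would take 28 per group. The stated 90% is reached only as a paired test on 16 patients (91.2% and 91.4%). So this statement names a comparison group the design lacks, and its power does not fit that comparison.

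**The case against.** The strongest reply is that nothing here is miscalculated. That 16 patients suffice for 5.65 points is true however many are enrolled, and a minimum for the primary test can coexist with a larger target. Over-powering harms neither the type I error nor the estimate, and precision improves. Even if half of the 40 lacked a 12-month score, power would still be 96.4%. The additional patients also serve the stated safety aim. All of this stands, and it limits the point to a missing link and a figure that does not describe the planned trial.

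Some stronger readings are tempting but not supported:

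- A reader might infer that 24 patients would be treated for no purpose. The documents support only that no reason is stated. Safety is a declared objective, and any allowance for loss brings the excess below 24.
- A reader might infer that the larger number is what allows a significant result below 5.65 points. At n = 16 an observed mean change of 2.131 × 6.38/√16 = 3.40 points is already significant. At n = 40 the threshold is 2.023 × 6.38/√40 = 2.04. The larger number lowers the threshold but does not create the property.
- A reader might infer that 40 is left over from a two-arm plan, since 2 × 16 = 32 and 32/0.8 = 40. The documents state neither a two-arm total nor a 20% loss, and that origin would not justify 40 in a single arm.

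The reply does not supply what is missing. The plan never calls 16 a minimum or 40 a ceiling; it labels 40 as the target.

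**Conclusion.** The point holds in limited form. Section V.12 correctly powers a 16-patient paired comparison, but the trial enrols 40 in one arm and the plan states neither its power at that size nor why that size was chosen. On the plan's own inputs, 40 patients give 99.98% power for 5.65 points and 90% power for about 3.35 points, or 3.77 with 32 evaluable. These figures rest on 6.38 being the SD of the change and on a two-sided test; the 32 rests on an assumed 20% loss.

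The trial is over-powered for its stated target, with no bias to the primary analysis. This is a mis-stated design figure and an unexplained enrolment number. It should be corrected, but it ranks below the faults that must be fixed before the trial can proceed.

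**What to change.** Keep the enrolment target of 40 and rewrite the sample-size text in Section V.12 to match it. State:

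- the number enrolled and the number expected to have a 12-month TSQ score, with the assumed loss;
- the TSQ difference detectable with 90% power at that evaluable number (3.35 points at 40; 3.77 at 32), and that the test is two-sided;
- that 6.38 is assumed to be the SD of the within-patient change;
- the purpose of the patients beyond 16, for example safety precision (zero-event upper limit of 8.8% at 40 against 20.6% at 16).

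In the same edit, replace the SF-36 comparison with thyroidectomy by a pre/post statement at the same number. Treating 9.7 and 11.0 as SDs of change (again an assumption) and scaling from the TSQ result, the differences detectable with 90% power at 40 are 3.354/6.38 × 9.7 = 5.1 points (Physical) and 3.354/6.38 × 11.0 = 5.8 points (Mental). At 32 they are 5.7 and 6.5.

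The cost is wording in one section, with no change to patients, visits or procedures. Cutting enrolment towards 16 plus an allowance would also remove the mismatch, but that is a change of design and would give up safety precision.
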